3.0 Planned trial interventions:

3.1 Intervention: In addition to standard care, participants randomized to the intervention arm will also receive the CardioPrevent® Program. This is a 1-year, evidence-based behaviour change lifestyle program that consists of 25 contacts (in person, by phone and in groups) with a trained lifestyle counsellor to facilitate desired lifestyle behaviours within the participants' own social context.

3.2 Control: Standard postpartum clinical care through the participants' usual healthcare providers.

3.3 All Participants: Participants in both arms will receive educational material about the risk of CVD, and CVD prevention for women with HDP from the Preeclampsia Foundation (*Appendix 6*).

3.4 Duration of Treatment: The treatment period is one year. This duration is clinically important for two reasons. First, longer behaviour change interventions have greater success with maintenance of healthy behaviours compared with shorter interventions⁴. Thus, the CardioPrevent® behaviour change

intervention was specifically designed to be one year⁵. Second, maternity leaves in Canada are generally one year. Women in the intervention arm will be in the “relapse prevention” phase of the behaviour change intervention as they return to work. The CardioPrevent® postpartum participants to date have emphasized the importance of this phase.

3.5 Duration and frequency of follow up: All study participants will complete in person clinical assessments at baseline, six months, and one year after their randomization date. All study assessments will be done on an individual basis, by a research assistant who is blinded to group assignment.

4.0 Study Outcomes:

4.1 Primary outcome:

a) *Study feasibility:* Acceptance of the study by women with HDP (i.e., feasibility) measured by all of the following: recruitment rate of $\geq 20\%$ over a 6-month time period (as per weekly recruitment logs –); participant adherence of $\geq 80\%$ to the lifestyle program (i.e., 20/25 contacts with counsellor completed); overall study completion rate of $\geq 75\%$ of participants; and participant satisfaction score of \geq fair on the Client Satisfaction Questionnaire at the end of study⁶.

b) *Implementation and fidelity of CardioPrevent® at a second centre* measured by standardized audits as well as similar clinical outcomes between sites

4.2 Secondary outcomes:

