5.7 Anticipated loss to follow-up: In the Family Heart Health Study (non-postpartum individuals), at one year, the rate of loss to follow-up was 27% in the standard care arm and 24.6% in the intervention arm (25% cited "too busy" or "not interested")³⁴. In the DEBI postpartum trial, however, there were higher rates of participant completion of the 1-year study: 90% in the intervention arm and 80% in the control arm; and 97% of participants in the intervention arm were "satisfied" with the program³⁵. Thus the target participant completion rate for the IMPROVE-Pilot study is $\geq 80\%$ (i.e., LTFU of <20%). To reach this target, we have also included reimbursements for parking and childcare costs for the baseline, 6- and 12-month outcome assessment visits. In addition, we have increased the study sample size by 30% to account for potential LTFU common to lifestyle intervention studies³⁴.

5.8 Sample size: A total of 84 women will be recruited (42 in each arm). This is based upon a minimally clinically important difference in BMI of 1 kg/m² supported by the literature on the association between BMI and CVD^{36, 37} and by the finding from the Canadian PE-NET cohort demonstrated that women with HDP actually increase their BMI by 1 year postpartum³⁸. Results of CardioPrevent® in other populations of women resulted in SD of 1.4-2.3³⁴. The lower SD of 1.4, alpha of 0.05 and power of 80% yields 32 women per arm (64 total). We increased this by 30% to account for loss to follow-up in other postpartum studies³⁵.

5.9 Recruitment: There are over 7000 deliveries per year at the FMC. Using a conservative estimate of 7% prevalence of HDP (as it is a tertiary care referral centre), approximately 245 women (10 per

week) will have HDP over our 6-month recruitment period. We anticipate recruiting 2-3 eligible women per week to reach our target sample size in 6 months. Recruitment will be monitored on a weekly basis with review of recruitment logs that monitors reasons for non-participation and ineligibility. Should recruitment rates from the in-patient wards alone be below anticipated targets, we will engage alternate modes of participant recruitment through outpatient clinics (Maternal Fetal Medicine and Obstetric Medicine) where we have co-investigators and recruitment infrastructure.

6.0 Statistical analyses: At the end of the study, the following will be analyzed.

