Participant characteristics will be summarized with standard descriptive statistics. *Feasibility outcomes* will be summarized as frequencies with % and presented as per CONSORT Guidelines³⁹, between group differences will be tested using Pearson's chi-square or Fisher's exact test. Non-adherence patterns will be assessed. *Quality assurance (QA) measures:* Mean with standard deviation (SD) scores from the three QA checks per counsellor will be compared to Ottawa standards using a Student's t-test. *Clinical outcomes:* Changes from baseline will be summarized using: means with SD; medians with interquartile ranges; and counts with % where appropriate. Exploratory analysis comparing outcomes between arms will be done with T-tests for continuous variables and chi-square or Fisher's exact tests for categorical variables. *Planned subgroup analysis:* will be performed to compare severity of HDP (gestational HTN, non-severe preeclampsia [PE], early onset PE < 34 weeks, or clinically severe PE) on clinical and vascular outcomes. An *intention-to-treat* principle will be followed. All *P-values* will be two-sided, at a significance level of 0.05. *Missing data* will be imputed.

7.0 Trial Management:

The trial will be managed through the Libin Cardiovascular Institute. A 0.4 FTE Research Coordinator will be responsible for the day-to-day conduct of the trial under the supervision of the study PI, including: REB applications; recruitment reports; and data quality reviews. A 0.1 FTE Research Nurse responsible for screening participants and obtaining informed consent. Data will be managed by Libin's Data Management Service, including: development of database; development of electronic case report forms; on-line randomization; and data maintenance and storage.

8.0 References:

1. Quorus Consulting Group. Cell phone consumer attitude study, prepared for the Canadian wireless telecommunications association. 2012;Jan 4 2012.
2. National Research Council. Weight gain during pregnancy: Reexamining the guidelines. *Washington DC: The National Academies Press.* 2009.

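### The only test stated for the feasibility outcomes compares the arms, but feasibility is defined by absolute thresholds, and two of the four criteria have no second arm to compare

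*Protocol*

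**What the plan says.** Protocol section 4.1(a) makes feasibility the first primary outcome, "measured by all of the following":

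- recruitment of at least 20% over six months, "as per weekly recruitment logs";
- adherence of at least 80%, explained as "20/25 contacts with counsellor completed";
- overall completion of at least 75%;
- a satisfaction score of at least "fair on the Client Satisfaction Questionnaire at the end of study".

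Section 6.0 (Statistical analyses) summarises feasibility outcomes as frequencies with percentages, presented according to CONSORT, and states that "between group differences will be tested using" Pearson's chi-square or Fisher's exact test. It names no other inference for them. The one comparison with an external standard in 6.0 is the t-test of counsellor quality scores against the Ottawa standards, which serves the separate fidelity outcome in 4.1(b).

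Under 5.1, women are screened, approached and consented on the ward and are randomised later, at the baseline visit. Under 3.1 and 3.2 the 25 counsellor contacts belong to the intervention and controls receive usual care; 5.3 confirms that controls have no direct access to the counsellor.

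The 84 women in 5.8 are not sized on any feasibility criterion: "This is based upon a minimally clinically important difference in BMI" of 1 kg/m².

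**The concern.** The criteria ask whether a single proportion, or a score, reaches a fixed value. The stated test asks whether two arms differ. For recruitment and adherence there are no two arms, so the test cannot be run. For completion, and for satisfaction if both arms answer, it can be run but answers another question.

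Feasibility is the first primary outcome of this pilot. A reader of the results would have percentages to set against the thresholds, and p-values that do not bear on them. With 42 women in the intervention arm and 84 overall, a percentage just above a threshold is compatible with a true value well below it, and nothing in the stated analysis shows this.

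**Working it through.** **1. The plan's own figure.** Section 5.8 uses a difference of 1 kg/m², SD 1.4, two-sided alpha 0.05 and power 80%.

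- Normal approximation: 2 × (1.960 + 0.842)² × 1.4² / 1² = 30.8, so 31 per arm.
- Solution based on the t-test: 31.76, so 32 per arm, as stated.
- Inflation by 30%: 32 × 1.3 = 41.6, so 42 per arm and 84 in total, as stated.

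The figure reproduces. It sizes a BMI comparison and gives no precision for the feasibility criteria.

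**2. Where the stated test can be applied.**

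| Criterion (4.1a) | Two arms? | Does a between-arm test address the threshold? |
|---|---|---|
| Recruitment ≥20% | No, counted before randomisation | Cannot be run |
| Adherence ≥80% | No, intervention arm only | Cannot be run |
| Overall completion ≥75% | Yes | No |
| Satisfaction ≥ fair | Only if both arms answer | No |

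**3. The p-value can point the opposite way from the criterion.** Two illustrative results for completion, Fisher's exact test:

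- 25/42 against 25/42: p = 1.00. Overall (25 + 25)/84 = 59.5%, below 75%.
- 42/42 against 34/42: p = 0.005. Overall (42 + 34)/84 = 90.5%, above 75%.

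**4. Precision of the bare percentages.** Exact (Clopper-Pearson) 95% limits for x of n are the 2.5% quantile of Beta(x, n − x + 1) and the 97.5% quantile of Beta(x + 1, n − x). Adherence is read as the share of intervention women who complete at least 20 of 25 contacts. For the smallest count that meets each criterion:

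- Adherence: 0.80 × 42 = 33.6, so 34/42 = 81.0%, CI 65.9% to 91.4%.
- Completion: 0.75 × 84 = 63, so 63/84 = 75.0%, CI 64.4% to 83.8%.
- Completion at the 80% target of 5.7: 0.80 × 84 = 67.2, so 68/84 = 81.0%, CI 70.9% to 88.7%.

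**5. Chance that one criterion is met when the true value is below it** (binomial tail):

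- P(X ≥ 34 | n = 42, p = 0.75) = 0.24; with p = 0.70 it is 0.08.
- P(X ≥ 63 | n = 84, p = 0.70) = 0.19.

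All criteria must be met, so each figure is an upper bound on the chance of declaring feasibility at that true value.

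**6. Recruitment.** 4.1(a) names no denominator. Section 5.9 expects 7000 × 0.07 / 2 = 245 women with HDP in six months; using 245 is an assumption.

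- At the threshold: 49/245 = 20.0%, CI 15.2% to 25.6%.
- At the planned enrolment: 84/245 = 34.3%, CI 28.4% to 40.6%, clear of 20%.
- If all deliveries screened were the denominator (5.6): 7000 / 2 = 3500, so 84 women would be 2.4%, and 20% would need 700 women.

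**The case against.** The strongest reply is that 6.0 first promises frequencies with percentages, which can be set directly against the thresholds. The between-group clause is an addition and is naturally read as applying only where two groups exist. Intervals could be added in an SAP that is not shown. This is fair, and it means that the absence of intervals alone would not be a finding. What stands is that the one inference 6.0 does state does not fit the outcome it is attached to.

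Three stronger readings are tempting, and the protocol does not support them.

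- *The p-value decides feasibility, or a go/no-go decision.* No such rule is written, and the protocol states no progression rule to a later trial.
- *An overall completion rate would hide a large gap between arms.* An overall 75% could be 38/42 against 25/42, but the planned Fisher test gives p = 0.002 for that split and would expose it. This is a reason to keep the test for completion.
- *Each arm should reach 75%.* Section 4.1(a) sets an overall rate, so a per-arm rule would rewrite the primary outcome.

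It is also fair to say that recruitment is not borderline under the plan if 245 is the denominator. A trial that stopped at 49 women would not have 42 per arm, so the recruitment case at its threshold does not go together with the other two examples.

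**Conclusion.** The concern holds in this form: the stated between-arm test cannot be applied to recruitment or adherence and does not address the thresholds for completion or satisfaction. A descriptive reading of the percentages remains possible, but it is imprecise. At its threshold, the interval for adherence reaches about 15 points below the observed value (81.0 − 65.9), and for completion about 11 points (75.0 − 64.4).

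This rests on full enrolment of 84 women split 42 and 42, on reading adherence as a share of women, and on counting all randomised women for completion. If adherence means the average percentage of contacts, the interval changes but the outcome is still confined to one arm. The change is worth making because it concerns the primary outcome and costs little; it does not call the design or the thresholds into question.

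**What to change.** First reconcile the completion criterion of at least 75% in 4.1(a) with the target of at least 80% in 5.7. Then, in 6.0:

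- Report recruitment, adherence and overall completion each as a single proportion with an exact 95% interval beside its threshold. State that the interval shows precision and is not a pass rule. A rule that the lower limit must reach the threshold would need 39/42 for adherence and 72/84 for completion at 75%, which 4.1(a) does not ask for.
- Name the denominators: for recruitment, the women with HDP (or the eligible women) in the recruitment log, not all deliveries screened; for adherence, all women randomised to the intervention; for completion, all randomised women.
- Report satisfaction on its score scale against the cut-off of fair, with its interval.
- Restrict the between-arm test to completion, and to satisfaction if both arms answer, as a check on differential attrition and not as the feasibility analysis. Keep completion as an overall rate.

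The cost is a few sentences, with no added women or data. The intervals will look less favourable than bare percentages.

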a) Comparison of the following *clinical outcomes* between both study arms at one-year of follow-up: weight, body mass index, waist-to-hip ratio, smoking status, postpartum depression, blood pressure, fasting lipids, fasting glucose, HbA1C, urine albumin to creatinine ratio, metabolic syndrome z-score and CVD risk.

b) *Microvascular function:* mean changes from baseline to one year of follow-up compared between groups for the following measures: flow mediated dilatation (FMD), brachial artery hyperemic velocity and peripheral arterial tonometry (PAT).

c) Changes in physical activity and dietary behaviour.

4.3 Measurement of study outcomes: Standardized assessments will be performed by a trained research assistant (blinded to group allocation) as outlined below, and in the Schedule of Measures (Appendix 8).

4.3.1 Clinical measures:

a) *Blood pressure:* Blood pressure is measured in a seated position after a five-minute rest period using an automated non-invasive blood pressure monitor (BPTru®) that automatically performs up to six measurements, discards the first reading, and displays the average of the subsequent readings⁷. Treatment of hypertension is determined by a review of current medication use.

b) *Body composition:* Height and weight are measured for the determination of body mass index (BMI) using a standardized protocol⁸. Waist and hip circumferences are measured using standard anatomical landmarks following the World Health Organization’s recommendations⁹.

c) *Smoking status:* Current smokers are defined as individuals who have smoked any cigarettes (even a puff) in the past seven days¹⁰. Claims of non-smoking are verified using a carbon monoxide analyzer (Bedfont Smokerlyser) with CO levels $< 10\text{ppm}$ confirmatory for non-smoking¹¹.

d) *Medication Use:* It is measured by having participants list the name and dosage of all prescription medications they are currently taking. Participants are asked to bring their medications with them to each visit for verification. Medication adherence with MAQ-8 questionnaire¹².

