5.1 Participant allocation and randomization: In order to maximize recruitment rates, a research nurse at FMC will screen admitted patients on the obstetrical wards for eligibility for the trial prior to discharge from hospital. The research nurse will then approach women who meet the eligibility criteria to explain the study and determine whether the women are interested in participating in the study. If a woman is interested, she will be provided with written information on the study. After providing informed consent, she will be given an appointment for the baseline assessment at approximately six weeks (range of 6 to 12 weeks) postpartum. After discharge from the hospital, participants will be sent reminder information about the study and the date of the baseline visit.

At the baseline assessment visit, consecutive women will be randomized to either the intervention or control arm in a 1:1 allocation, with use of permuted blocks of variable length (2, 4 or 6) using an on-line central randomization system through the Data Management Services group at the Libin Cardiovascular Research Institute. The on-line randomization program will ensure participant eligibility and maintain concealment of allocation. The randomization schedule will be prepared by an independent statistician using a computer-generated random number scheme.

5.2 Blinding - the outcome assessor and statistician: The nature of the intervention (i.e., the CardioPrevent® cognitive-behavioural lifestyle counsellor) does not lend itself to blinding of the participant. However, the research assistant responsible for the outcome assessments will be blinded to each participant's group allocation and will be instructed not to ask any questions pertaining to the study intervention. The study statistician will also be blinded to group allocation.

5.3 Contamination: Contamination is unlikely, as individuals allocated to the control group will not have direct access to the cognitive-behavioural lifestyle counsellor. It is possible, however, that participants may know other women involved in the study. Consequently, participants in both arms will also be instructed not to share their study information with other participants.

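### Section 6.0 commits to unadjusted t-tests although a baseline is collected, and leaves open whether clinical outcomes are tested as one-year values or as changes

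*Protocol*

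**What the plan says.** Section 6.0, under clinical outcomes, first describes the summary: "Changes from baseline will be summarized using: means with SD; medians with interquartile ranges". The next sentence gives the between-arm test: "Exploratory analysis comparing outcomes between arms will be done with T-tests for continuous variables". It names neither the scale tested nor any covariate.

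Section 4.2 defines the secondary outcomes in three groups:

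- 4.2(a), clinical outcomes such as weight, BMI, blood pressure and lipids, are compared "between both study arms at one-year of follow-up". Change is not mentioned. The list ends with "urine albumin to creatinine ratio, metabolic syndrome z-score and CVD risk".
- 4.2(b), vascular measures, are stated as "mean changes from baseline to one year of follow-up compared between groups".
- 4.2(c) reads "Changes in physical activity and dietary behaviour".

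Section 3.5 provides for "in person clinical assessments at baseline, six months, and one year after their randomization date", and section 5.1 says "At the baseline assessment visit, consecutive women will be randomized", so a baseline assessment is part of the design for every randomised woman. Section 5.1 uses permuted blocks and names no stratification factor. Section 5.8 sizes the trial on a BMI difference of 1 kg/m² with SD 1.4, the lower end of a range of 1.4 to 2.3, and does not say whether these are SDs of BMI or of BMI change.

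**The concern.** The protocol does not leave the method to a later plan. It names a t-test, and that test ignores a measurement taken on every woman. Two consequences follow.

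**Scale.** For the 4.2(a) outcomes, the outcome definition points to one-year values and the analysis section leans towards changes. Sections 4.2(b) and 4.2(c) cover different outcomes, so they do not contradict 4.2(a), but they show that the authors write change when they mean it. The two t-tests can differ greatly in power, and leaving the choice open allows it to be made after the data are seen.

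**Precision.** A model with the baseline value is at least as precise as either t-test, apart from one degree of freedom, and it removes the effect of chance baseline imbalance. Nothing in the allocation balances baseline values. In a trial this small, that precision is worth having.

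No feasibility or fidelity conclusion, which are the primary outcomes, depends on this.

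**Working it through.** **Inputs from the protocol.** BMI difference 1 kg/m², SD 1.4, 80% power, 32 per arm (section 5.8); two-sided 0.05 (section 6.0).

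**Assumed, because the protocol gives no figure.** Baseline to one-year correlation ρ of 0.5, 0.7 and 0.8; ratio k of one-year SD to baseline SD of 1, with 0.8 and 1.25 as a check; SD of BMI values of 4 to 6.

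**The plan's own figure.** A two-sample t-test with standardised difference 1/1.4 needs 31.8 per arm for 80% power. At 32 per arm the power is 80.3%. The stated size therefore reproduces as an unadjusted t-test, provided that 1.4 is the SD of the quantity tested.

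**Variance of the arm effect, equal SDs, in units of the value's variance.**

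- t-test on one-year values: 1
- t-test on change: 2(1 − ρ)
- baseline-adjusted model: 1 − ρ², times 1 + 1/(64 − 4) = 1.0167 for estimating the slope

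So the adjusted model's variance is (1 − ρ²) × 1.0167 of that for one-year values, and (1 + ρ)/2 × 1.0167 of that for change.

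| ρ (assumed) | ratio to one-year values | ratio to change |
|---|---|---|
| 0.5 | 0.75 × 1.0167 = 0.762 | 0.75 × 1.0167 = 0.762 |
| 0.7 | 0.51 × 1.0167 = 0.518 | 0.85 × 1.0167 = 0.864 |
| 0.8 | 0.36 × 1.0167 = 0.366 | 0.90 × 1.0167 = 0.915 |

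A simulation of 20,000 runs with estimated slope gave 0.760, 0.526 and 0.367 against values, and 0.763, 0.860 and 0.924 against change. Against change, the gain vanishes once ρ exceeds 0.967.

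**Detectable difference at 80% power, 32 per arm, in SDs of the value.** The t-test on one-year values detects 0.71. Multiplying by √(2(1 − ρ)) gives 0.71, 0.55 and 0.45 for change. Multiplying by √((1 − ρ²) × 1.0167) gives 0.62, 0.51 and 0.43 for the adjusted model.

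**Unequal SDs.** The ratio to change is k²(1 − ρ²)/(k² + 1 − 2ρk) × 1.0167. Over the three correlations it is 0.58 to 0.65 at k = 0.8 and 0.91 to 1.02 at k = 1.25. The worst case is about the cost of the degree of freedom.

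**BMI, reading 1.4 as the SD of change.** Then ρ = 1 − 1.4²/(2 × SD²), which is 0.939 at SD 4 and 0.973 at SD 6. The ratio to change is 0.986 to 1.003, so the gain is close to nil. The scale, however, matters a great deal:

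| SD of BMI values (assumed) | power, one-year values | power, change | power, adjusted model |
|---|---|---|---|
| 4 | 17% | 80% | 81% |
| 5 | 12% | 80% | 80% |
| 6 | 10% | 80% | 80% |

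**Chance imbalance.** With 32 per arm, the standard error of a baseline mean difference is √(2/32) = 0.25 SD. A difference larger than that arises by chance in about 32% of trials for any one outcome.

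**Same effect on either scale.** Subtracting the baseline from the outcome changes only the baseline coefficient (by −1) when baseline is in the model. The arm coefficient and its standard error are unchanged.

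**The case against.** The strongest reply is that nothing here is invalid. The t-test is sound under randomisation, the comparisons are labelled exploratory, and the trial is a pilot for feasibility and fidelity. That stands and limits the importance of the point.

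Second, section 6.0 can be read as testing change, since the summary sentence comes just before the test, and the wording in 4.2(a) can be read as a time point. On that reading the large gains against one-year values fall away, leaving 8.5% to 24% at the assumed correlations and almost nothing for BMI, the one outcome used for sizing. This is a fair reading, but 4.2(a) does not say change, and the text does not settle it. A statistical analysis plan, which is not at hand, could name the scale; the protocol would still commit to a test without the baseline.

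Third, the imbalance figure is simply the chance of exceeding one standard error, and the t-test's own standard error already covers that variation. At the 42 per arm randomised, the standard error is √(2/42) = 0.218 SD and the chance of exceeding 0.25 SD is 25%. This is correct: the figure shows how large chance imbalance can be, not a bias.

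Fourth, a log-scale model for skewed outcomes combines two changes, transformation and adjustment, so its power gain should not be credited to adjustment alone; and the metabolic syndrome z-score can be negative and cannot be logged. Both points stand, and no skewness gain is counted here.

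Fifth, food logs are prospective and randomisation takes place at the baseline visit, so a baseline for 4.2(c) that precedes disclosure of the allocation is not assured by the text. This may need a small procedural step.

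**Conclusion.** The point holds. Section 6.0 commits to a test that leaves out a baseline collected by design, and for the 4.2(a) outcomes the protocol does not fix whether values or changes are tested. The gain in precision is modest against a change-score t-test (8.5% to 24% of variance at ρ 0.8 to 0.5 with equal SDs, near nil for BMI, at worst a loss of about 2%) and larger against one-year values (24% to 63%). These sizes rest on assumed correlations and SD ratios, because the protocol gives none. The unsettled scale matters most for BMI: if 1.4 is an SD of change, power at 32 per arm is 80% on change but only 10% to 17% on one-year values with an assumed BMI SD of 4 to 6. The change is worth making because it costs almost nothing; it affects secondary, exploratory results only.

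**What to change.** In section 6.0, for each continuous outcome measured at baseline, replace the t-test with a linear model of the 12-month value on arm and the baseline value of that outcome, reporting the adjusted mean difference with 95% CI. Use this one model for the continuous measures in 4.2(a), 4.2(b) and 4.2(c). For positive, skewed measures named in advance, such as triglycerides and the urine albumin to creatinine ratio, fit the model on the log scale and report a ratio with 95% CI; keep the metabolic syndrome z-score on its own scale. State that the baseline is recorded before allocation is disclosed. The descriptive summaries of change can stay.

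In section 5.8, say whether the SD of 1.4 to 2.3 is an SD of change or of values, because 32 per arm gives 80% power only if 1.4 is the SD of the quantity tested.

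The cost is one or two sentences in section 6.0, a phrase in section 5.8, and one degree of freedom per outcome (about 1.7% of variance at 64 completers). No new visits or participants are needed. The one practical matter is the timing of the baseline diet and activity records relative to disclosure of the allocation.
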